- Have unresolved injuries or trauma at the time of study entry.
- Having undergone surgical, non-ophthalmologic procedures within the past 3 months.
- Have received doses of vaccine against the Influenza virus or Coronavirus, 7 days prior to the inclusion of this study, or plan to receive it during the study intervention.
- Be or have an immediate family member (e.g., spouse, parent/legal guardian, sibling, or child) who is employed by the research site or sponsor, and who is directly involved in this study.
- Positive smoking (specified as cigarette smoking regardless of quantity and frequency, 4 weeks prior to study inclusion and during the study intervention period).
- Positive alcoholism (specified as the consumption of alcoholic beverages, regardless of quantity and frequency, 72 hours prior to the inclusion of the study and during the study intervention period).

Elimination criteria:

- Withdrawal of the informed consent form.
- Presentation of serious adverse event, whether or not related to the interventions, that, in the judgment of the Principal Investigator (PI) and/or sponsor, could affect the patient's ability to safely continue with study procedures.
- Non-tolerability or hypersensitivity to any of the compounds used during the tests (fluorescein, tetracaine).
- No tolerability or hypersensitivity to any of the investigational drugs.
- Adherence < 80% determined by the subject's diary and corroborated by the final weight of the research products (PI) with respect to the initial weight.

Duration of treatment: 7 days	Duration of the subject in the study: 13 days
Interventions:	

 • Investigational product, dosage, and route of administration: 
 - PRO- 231 . Moxifloxacin 0.5% Ophthalmic Solution. Laboratorios Sophia, S.A. de C.V. Zapopan, Jalisco, Mexico. - Dosage: 1 drop every 6 hours (3 daily applications [TID], in the right eye [OD]). - Route of administration: Topical ophthalmic. • Comparator product, dosage and route of administration: 
 - VIGAMOXI ® Moxifloxacino 0.5% Solución oftálmica. Alcon Laboratories, Inc., Fort Worth, Texas, USA. - Dosage: 1 drop every 6 hours (TID) in OD. - Route of administration: Topical ophthalmic. 	
Evaluation criteria:	

Primary outcome variables:***Safety***

- Incidence of Intervention-Related Unexpected AEs (Time to Assessment [ET]: Days 3, 8, and 12)

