- Incidence of conjunctival hyperemia and chemosis. (TE: day 3 and 8)
- Changes in the AVMC evaluated with the Snellen chart. (TE: day 3 and 8)
- Changes in ocular surface integrity using fluorescein staining, using the Oxford scale. (TE: day 3 and 8).

Tolerability

- ICO score changes. (TEE: day 8)

Secondary outcome variables:***Safety:***

- Incidence of expected and intervention-related AEs (excluding conjunctival hyperemia and/or chemosis). (TE: day 3, 8 and 12)

[figure not shown]
Tolerability:

- Presence of eye symptoms (burning, foreign body sensation, pruritus and tearing). (TE: day 3 and 8)

Statistical methodology

The analysis of the data collected in the study will be carried out by means of specialized statistical software (SPSS available version or R software). The data will be expressed with measures of central tendency: mean, standard deviation and/or ranges for quantitative variables, and frequencies and/or percentages for qualitative variables. The Shapiro-Wilk test (S-W) will be used to determine if the distribution is normal in the data obtained in each study group ($p>0.05$). If the normality in the distribution of the data is verified, to rule out differences between groups, the Student's t-statistic will be used for independent groups, while intragroup differences will be analyzed with the Student's t-test for repeated measures. In case of $p<0.05$ in S-W, the statistical analysis to rule out differences between groups will be performed by means of the Mann-Whitney U test for quantitative variables, while intragroup differences will be performed by Wilcoxon's rank test. The difference between the qualitative variables will be analyzed by means of the χ^2 statistic (Chi-squared) or Fisher's exact (for expected values less than 5). Dichotomous variables will be analyzed by the McNemar test when applicable. An alpha (α) ≤ 0.05 will be considered as statistical significance, in addition to this, the 95% CI will be calculated for these differences. For primary outcome variables, H_0 will be rejected, when $p \leq 0.05$ and the 95% CI does not include zero.

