7.4.3 Definition of variables, methods and scales for their measurement

Board 2. Operational definition of variables

Variable	Conceptual Definition	Operational Definition	Measurement Type	Reference value	Statistical test
Incidence of Intervention-Related Unexpected AEs	Any adverse medical event that occurs in the clinical research subject to whom any of the interventions were administered and that has a certain coincidental relationship to the interventions [33]	All AEs (according to protocol) in which the PI suspects a causal relationship with the interventions will be reported	• Discrete quantitative • Nominal qualitative	• Relationship with IP • Severity • Causality	
 • Student's t-test of independent groups • U de Mann Whitney* • Pearson X² or Fisher Exact*
Incidence of conjunctival hyperemia	It is the reaction of the conjunctiva to a stimulus, a red appearance secondary to the vasodilation of the conjunctiva vessels of variable intensity is seen	Direct observation. Classification by Efron scale. See attachment 16.2. Efron Scale for Conjunctival Hyperemia	Degrees: 0 = Normal, I = Muy live, II = Mild, III = Moderate and IV = Severe		
 • Pearson X² or Fisher Exact* • McNemar Test*
Incidence of Chemosis	It is defined as conjunctival edema, the result of an inflammatory reaction. It is classified as present or absent	The evaluator will use a narrow beam of light at 60° and will measure whether the conjunctiva separates ≥ 1/3 of the total	• Nominal qualitative	Present / Absent	
 • Pearson X² or Fisher Exact* • McNemar Test*

Variable	Conceptual Definition	Operational Definition	Measurement Type	Reference value	Statistical test
Changes in the AVMC	Visual spatial acuity is the ability to distinguish separate elements of an object and identify them as a whole. It is quantified as the minimum angle of separation (located at the nodal point of the eye) between two objects that allows them to be perceived as separate objects	eyelid opening or if it exceeds the gray line Cartilla de Snellen. Ver anexo 16.5 Fraction to LogMAR conversion table.	• Continuous quantitative	20/30 (0.2 LogMAR) or better	
 • Student's t-test of independent groups • U de Mann Whitney*

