7.4.4.1 Conjunctival hyperemia

It is defined as the simplest reaction of the conjunctiva to a stimulus, with a red appearance secondary to vasodilation of the conjunctival vessels of variable intensity. It will be graduated using the Efron scale. See annex [38][16.2. Efron Scale for Conjunctival Hyperemia](#)

The PI will record in the file and the eCRF the grade, in grades (Grade 0 = normal, grade 1 = traces, grade 2 = mild, grade 3 = moderate, grade 4 = severe), granted for conjunctival hyperemia OD and OS respectively.

Management as AE: An adverse event will be considered when the grade is greater than or equal to grade 3 (moderate).

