7.4.4.2 Chemosis

It is defined as conjunctival edema, the result of an inflammatory reaction. It is qualified as present or absent. The evaluator will use a narrow beam of light at 60° and will measure whether the conjunctiva separates from the sclera by $\geq 1/3$ of the total eyelid opening or if it exceeds the gray line. [39]

The PI will record in the file and the eCRF if the chemosis is absent or present.

Management as AE: An adverse event will be considered when present.

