7.4.4.6 Adverse events

As described in the [8. Evaluation and management of adverse events](#) An adverse event is defined as any unfavorable medical occurrence in a subject to whom an investigational product is administered, regardless of causal attribution.

Adverse event management shall be carried out as described in section [8. Evaluation and management of adverse events and incidents](#).

The Principal Investigator will record in the corresponding section of the eCRF the adverse events that the study subjects may present in addition to referring them in the clinical record.

For an adequate evaluation of adverse events, in addition to directed questioning, it is necessary to perform a comprehensive ophthalmological evaluation at each visit, which consists of: ophthalmological examination of the eyelids and adnexa; anterior and posterior segment that is performed in a routine ophthalmological check-up, whose procedures are not specifically included in the study variables. Posterior pole evaluation can be with direct or indirect ophthalmoscopy, with or without pharmacological mydriasis, at the discretion of the PI. An assessment of the fundus will be carried out in search of abnormalities that alter the result of the study. IOP will be measured in this evaluation, with the Goldmann tonometer, it should be measured after the evaluation of stains. The result of the assessment will be recorded in the clinical file. In the eCRF, only findings that are considered so by the Principal Investigator will be reported as an adverse event.

The ocular adverse events that can occur with PRO-231, according to what is reported in the literature, are: ocular burning, dysgeusia after instillation, foreign body sensation, ocular pruritus, conjunctival hyperemia, chemosis, photophobia and whitish corneal precipitates. The frequency of systemic adverse events with ophthalmic fluoroquinolone administration is low.[\[1, 13\]](#) [\[1\]](#)

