7.7.5 Unscheduled follow-up visits

At the request of the subject or personnel related to the study, unscheduled follow-up visits may be carried out for the reporting of adverse events or any situation that warrants it. During these visits, all pertinent data on the adverse events reported should be collected and, where appropriate, an appropriate management plan should be established.

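### Hyperemia or chemosis at adverse-event level that clears before the Day 3 or Day 8 exam, or starts after Day 8, is reported as an AE but enters no named between-arm endpoint

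*Combined protocol and SAP*

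**What the plan says.** All references are to the combined protocol and SAP.

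- **Sign variable (primary).** The synopsis gives "Incidence of conjunctival hyperemia and chemosis. (TE: day 3 and 8". Section 7.4.1.1 lists the same variable without times. Table 2 (section 7.4.3) defines hyperemia by "Direct observation. Classification by Efron scale". For chemosis, section 7.4.4.2 says "The evaluator will use a narrow beam of light at 60° and will measure whether the conjunctiva separates" from the sclera by a set amount. Neither definition uses the subject's recall.
- **When a sign is an AE.** For hyperemia, section 7.4.4.1 says "An adverse event will be considered when the grade is greater than or equal to grade 3 (moderate". Under section 7.4.4.2 any chemosis is an AE.
- **AE variables.** The primary one is "Incidence of Intervention-Related Unexpected AEs (Time to Assessment [ET]: Days 3, 8, and 12". The secondary one is "Incidence of expected and intervention-related AEs (excluding conjunctival hyperemia and/or chemosis). (TE: day 3, 8 and 12". The exclusion is repeated in sections 3.1.2.2 and 7.4.2.1 and in Table 2.
- **Expectedness.** Section 7.4.4.6 names "conjunctival hyperemia, chemosis, photophobia and whitish corneal precipitates" among the events that can occur with PRO-231.
- **AE collection outside the two exams.** Section 7.7.5 says "unscheduled follow-up visits may be carried out for the reporting of adverse events or any situation that warrants it". The Day 12 contact (section 7.7.4) is a telephone call for AEs only.
- **Analysis.** Primary variables use the per-protocol population (10.3.2.1) and secondary variables use all treated subjects (10.3.2.2). The decision table in 10.3.1 reads a p-value of 0.05 or more, with a confidence interval that includes zero, as showing the treatments to be similar.

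**The concern.** Hyperemia and chemosis were taken out of the secondary AE variable, presumably because they have their own primary variable and should not be counted twice. But the two variables do not cover the same time. The sign variable looks on two days; the AE variables run to Day 12 and receive reports from between visits. What the exclusion removes is therefore wider than what the sign variable picks up.

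Section 10.1 names hyperemia among the common moxifloxacin AEs and calls most of these events mild and transient, and two fixed exams are poorly suited to short episodes. If the same fraction f of episodes is seen in both arms, the observable difference shrinks from pA − pB to f × (pA − pB). Under the decision table in 10.3.1, a smaller difference makes a finding of similarity more likely. Section 8.3 calls the measurement of safety paramount, so related events that the trial itself records should have a defined place in the comparison.

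**Working it through.** The plan states no figure on this point, so there is none to reproduce. The main check is a trace of the definitions. The arithmetic after it is illustrative.

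**1. Trace one case.** A subject has related grade 3 hyperemia on Day 5, is seen at an unscheduled visit, and is clear on Day 8.

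- Primary sign variable: assessed on Days 3 and 8 by observation. The sign is absent on both days, so it is not counted.
- Primary AE variable: unexpected related AEs only. Hyperemia is on the list in 7.4.4.6, and the reaction tables in 2.1 also list red eye and conjunctival edema. Not counted.
- Secondary AE variable: expected related AEs, with hyperemia and chemosis excluded. Not counted.
- Ocular symptoms (7.4.4.3): these do use recall since the last visit, but ask only about burning, foreign body sensation, itching and tearing. Not counted.
- Eye Comfort Index: a symptom score completed at baseline and at the final visit. It does not record a hyperemia or chemosis AE.

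An AE-level episode that starts after the Day 8 exam and is first reported at the Day 12 call follows the same path. An episode that starts between visits and persists to Day 3 or Day 8 is counted.

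**2. Text that points the other way.**

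- Table 2 describes the unexpected-AE variable operationally as all AEs that the investigator suspects are caused by the interventions. The word unexpected appears only in the variable's name.
- In Table 5, row E1 is labelled simply as incidence of AEs, and its footnote covers AEs whether or not they are related. It does not repeat the exclusion.

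Read alone, either text could admit the Day 5 episode. Both conflict with the endpoint names, which carry the restriction to unexpected events and the exclusion. Neither says that hyperemia or chemosis is put back.

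**3. Share of episodes that two exams miss (illustration).** Assumptions that are not in the documents: one episode per subject, start day s equally likely on Days 1 to 7, and duration d whole days (present on days s to s + d − 1). The exams are on Days 3 and 8. An episode is caught if Day 3 or Day 8 lies in its span; the missed share is 1 − (start days caught)/7.

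- d = 1: caught for s = 3; missed 1 − 1/7 = 6/7 (86%).
- d = 2: caught for s = 2, 3, 7; missed 1 − 3/7 = 4/7 (57%).
- d = 3: caught for s = 1, 2, 3, 6, 7; missed 1 − 5/7 = 2/7 (29%).
- d = 4: caught for s = 1, 2, 3, 5, 6, 7; missed 1 − 6/7 = 1/7 (14%).

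Visit 1 has a window of ±1 day. Moving it to Day 2 or Day 4 leaves d = 1 and d = 2 unchanged. For d = 3 the missed share is 3/7 (Day 2) or 2/7 (Day 4). For d = 4 it is 2/7 (Day 2) or 0 (Day 4).

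**4. What these shares measure.** They apply to episodes of any grade and describe the limit of two timed exams. They do not measure the effect of the AE exclusion, because hyperemia below grade 3 between visits is not an AE under 7.4.4.1 and need not be recorded at all.

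**The case against.** Timed slit-lamp grading is a legitimate choice, and keeping signs apart from AEs avoids double counting. Both points stand; the trouble is only that the exclusion is wider than the exams that replace it.

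A reader might infer more than the documents support:

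- *That these episodes disappear from the safety evaluation.* They do not. Grade 3 or higher hyperemia and any chemosis are recorded and followed as AEs, and sections 8.5 and 8.5.3 put AEs into the final report. What is missing is a defined between-arm comparison.
- *That no text could bring them in.* Table 2 and the Table 5 footnote could be read that way. Unexpected is not formally defined either, so an episode of unusual severity, or one recoded to a diagnosis under 8.5.2.1, might enter an AE variable. The accurate finding is a gap in the named endpoints together with conflicting text.
- *That incidence is understated by 86% or 57%.* Those shares rest on assumed onset and duration and on isolated episodes. Dosing is repeated daily for 7 days, so persistence or recurrence is possible.
- *That one arm is favoured.* Nothing in the documents shows different timing or duration of episodes by arm.
- *That Day 12 hides many events.* The call comes about five days after the last dosing day (Day 7), and the documents give no rate for late onset.

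It is also fair to object that mild redness, which motivates much of the worry, would stay uncounted after any change that relies on AE records. Nor can a telephone report be graded on the Efron scale or checked with a slit beam. Both limits stand and are carried into the fix.

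**Conclusion.** The point holds in a limited form. On the endpoint names, an AE-level episode of hyperemia (Efron grade 3 or more) or chemosis that resolves before the Day 3 or Day 8 exam, or first appears after Day 8, is recorded and reported but belongs to no named between-arm endpoint. This rests on two readings: that the synopsis timing governs the sign variable (it is printed only there, but the observation-based definitions and the visit schedule agree with it), and that events listed in 7.4.4.6 are not unexpected.

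The number of events affected cannot be derived from the documents. The 6/7 to 1/7 range for 1-day to 4-day episodes shows only that short episodes are easily missed by two exams. Because the events remain in the AE record and the remedy uses data already collected, this is a cheap improvement and not a condition for a valid trial. The conflict among the endpoint names, Table 2 and Table 5 should be settled in any case.

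**What to change.** 1. Keep the graded Day 3 and Day 8 findings as the by-visit primary variable.
2. Add a between-arm comparison, in all treated subjects as defined in 10.3.2.2, of the proportion with AE-level hyperemia or chemosis at any time from first dose to the Day 12 call. State the case threshold: hyperemia of Efron grade 3 or more at a scheduled exam or unscheduled visit, or hyperemia recorded as an AE by the investigator; or any chemosis. Flag cases known only from the call, which have no Efron grade or slit-beam check.
3. Alternatively, close the same gap by limiting the exclusion in the secondary AE variable to events already counted at the Day 3 and Day 8 exams.
4. Reconcile Table 2's operational definition of the unexpected-AE variable and the Table 5 footnote with the endpoint names, and repeat the assessment times in section 7.4.

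The cost is wording in the synopsis, sections 7.4.1 and 7.4.2 and Tables 2 and 5, plus one more comparison, all settled before unblinding. It needs no extra visit, procedure or subject. The downside is that some counted cases will rest on ungraded reports, and milder redness between visits will remain uncounted.

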1.2 Study diagram

1.3 Subject Timeline

Procedures	Scrutiny / Basal	Visit 1	Final Visit	Call Security
	Visit			
	Day 0	Day 3 ± 1	Day 8	Day 12 ± 1
Signing the informed consent form	X			
Comprehensive medical history	X			
Ophthalmological medical history	X			
Urine pregnancy test	X		X	
Eligibility Criteria	X			
Eye symptoms	X	X	X	
AVMC Measurement	X	X	X	
Previous Segment Evaluation	X	X	X	
Fluorescein staining evaluation	X	X	X	
Intraocular pressure measurement	X	X	X	
Posterior Segment Evaluation	X		X	
Subject and IP code assignment	X			
Delivery of the PIs and indicate the start of application the next day (day 1)	X			
Return of IP			X	
Adherence assessment		X	X	
Evaluation of adverse events	X	X	X	X
Eye Comfort Index	X		X	
Subject Diary Delivery	X			
Return / Evaluation of the subject's Journal			X	
Subject continuity assessment	X			

Abbreviations: AVMC, best corrected visual acuity; PI, research products.

2. Introduction and background

2.1 Theoretical framework

Humans are exposed to a variety of microorganisms, including bacteria, viruses, and fungi. In most cases, these microorganisms do not cause infection thanks to the external barriers (skin and mucous membranes) that protect us from their invasion, and the immune system. However, some microorganisms can directly invade these external barriers or be introduced into the body through surgical or traumatic wounds; Additionally, the patient's immune system may be compromised, allowing microorganisms, which do not normally cause any problems, to generate an infection. [1]

Various compounds have been used to help the immune system fight pathogenic microorganisms. An important property of anti-infective drugs is their selective toxicity, eliminating microorganisms while causing minimal or no adverse reactions to the host. [1]

These drugs are not usually active against all species of microorganisms in the same category; The species against which the drug shows intrinsic activity is called *Spectrum of activity* of the drug. Narrow-spectrum drugs are only effective against a few species of microorganisms, while broad-spectrum drugs have activity against a wide variety of species. At the same time, microorganisms can develop resistance mechanisms against drugs to which they were originally susceptible, limiting the effectiveness of anti-infective drugs. [1]

Bacteria are the largest contributor to eye infections in the world and can affect different eye structures causing conjunctivitis, keratitis, endophthalmitis, blepharitis, orbital cellulitis and dacryocystitis. [2, 3]

Bacterial conjunctivitis is one of the most common eye infections and is estimated to account for up to 1% of consultations at the first level of care. It is characterized by eye discomfort, conjunctival injection, and mucopurulent discharge, and has a significant economic and social impact, as a result of disruption of the patient's normal activities, as well as absenteeism from work and/or school. It is usually self-limiting (duration of 1 to 2 weeks); however, empirical treatment with broad-spectrum anti-infective drugs is recommended to shorten the course of the disease, improve patient comfort, decrease transmissibility, promote early return to work or school, and reduce the risk of serious complications that may compromise vision [1, 2, 3, 4, 5, 6, 7]

The pathogens most commonly implicated in bacterial conjunctivitis include strains of *Staphylococcus aureus*, *Streptococcus pneumoniae*, *Streptococcus viridians*, *Haemophilus influenzae*, *Serratia marcescens* and *Pseudomonas aeruginosa*. [8, 9]

Although broad-spectrum topical antibiotics are usually used empirically, several factors need to be considered when selecting a treatment, such as how quickly it kills the pathogen causing the infection, how well it penetrates eye tissues, and the potential impact on the development of bacterial resistance. [9]

Moxifloxacin is a broad-spectrum antimicrobial that belongs to the fourth generation fluoroquinolones and thanks to its 8-methoxy group, it has improved activity against strains of *Streptococcus* and *Staphylococcus*, as well as moderate to excellent activity against gram-negative organisms that cause ocular pathologies. [6]

Moxifloxacin is a dose-dependent bactericide. Like the other fluoroquinolones, it interferes with the bacterial life cycle by binding to DNA gyrase (topoisomerase II) and topoisomerase IV. Both are essential enzymes for the replication, translation, repair, and recombination of bacterial deoxyribonucleic acid (DNA). Human cells lack these enzymes, so they are not affected by fluoroquinolones.[6, 8, 9, 10] [1, 8]

The antimicrobial activity or spectrum of fluoroquinolones will depend on their class, due to the variation in affinity and binding strength to topoisomerases, as well as to the bacterial species. [10]

They are generally well-tolerated drugs with a low incidence of adverse reactions after systemic administration. When they occur, these reactions are usually mild and reversible, the most common being: gastrointestinal (nausea, vomiting and diarrhea), dermatological (rash, urticaria, pruritus) and central nervous system (headache). However, they have also been associated with serious adverse events, including *Clostridium difficile*, prolongation of the QT interval, tendinitis, dysglycemia, liver toxicity, phototoxicity, acute renal failure and seizures. [1, 8, 11, 12]

The frequency of adverse events with topical fluoroquinolone administration is low; The most frequent ocular adverse reactions reported after the application of the 0.5% moxifloxacin ophthalmic solution are: decreased visual acuity, dry eye, keratitis, eye discomfort, ocular hyperemia, eye pain, pruritus, subconjunctival hemorrhage, tearing and burning. The most frequent non-ocular adverse events reported are: dysgeusia, fever, cough, otitis media, pharyngitis, rash and rhinitis. . [1][13, 14]

The following adverse reactions have been reported during clinical studies with Moxifloxacin 5 mg/mL ophthalmic solution and are classified according to the following criteria: very common, occurring in 1 or more in 10 patients ($\geq 1/10$); common, occurring in 1 or more in 100 patients ($\geq 1/100$ to $< 1/10$); rare, occur in 1 or more in 1,000 patients ($\geq 1/1,000$ to $< 1/100$); rare, occurring in 1 or more in 10,000 patients ($\geq 1/10,000$ to $< 1/1,000$); very rare, there is less than one case in every 10,000 patients ($< 1/10,000$); or unknown frequency (a number cannot be estimated from the available data). Adverse reactions are ordered by organ or system affected, from the most severe to the mildest: [15, 16, 17]

Classification by organs and systems	Frequency	Adverse Reactions [MedDRA Preferred Terms (v.15.1)]
Blood and lymphatic system disorders	Strange	Decreased hemoglobin
Nervous system disorders	Rare	Headache
	Strange	Paresthesia (tingling or numbing sensation)
Eye disorders	Common	Eye pain, eye irritation

	Rare	Dry eye, conjunctival hemorrhage, red eye, itchy eyes, eyelid edema (swelling of the eyelids), eye discomfort.
	Strange	Corneal alteration, conjunctivitis, blepharitis (inflammation of the edge of the eyelids), conjunctival edema, blurred vision, decreased visual acuity, asthenopia (visual fatigue), redness of the eyelids.
Respiratory disorders	Strange	Nasal discomfort, pharyngolaryngeal pain (sore throat), foreign body sensation in the throat
Gastrointestinal disorders	Rare	Dysgeusia (bad taste in the mouth)
	Strange	Vomit

Additional adverse reactions identified in post-marketing surveillance include the following: frequency cannot be estimated from available data. Within each classification by organ and system, adverse reactions are presented from the most serious to the mildest. [15, 16, 17]

Classification by organs and systems	Adverse reactions [MedDRA preferred terms (v.15.1)]
Immune system disorders	Hypersensitivity (allergic reactions)
Nervous system disorders	Seasickness
Eye disorders	Corneal ulcers, increased tearing, photophobia (sensitivity to light), eye discharge.
Heart disorders	Palpitations
Respiratory disorders	Dyspnea (shortness of breath)
Gastrointestinal disorders	Nausea
Skin disorders	Erythema (redness of the skin), purito (itching), rash (hives or blisters on the skin), hives (reddish hives that may cause itchy skin)

Available ophthalmic fluoroquinolones are indicated for the treatment of bacterial conjunctivitis and keratitis, with a treatment regimen of one drop three times daily for 7 days (the total duration of therapy will depend on the severity of the clinical picture and the course of the infection). In addition, they have been used off-label as prophylaxis in surgical procedures and ocular trauma to prevent endophthalmitis. However, because new molecules such as gatifloxacin and moxifloxacin have a higher spectrum and lower resistance, they should be reserved for the treatment of more severe eye infections.[8, 9, 15, 16] [17, 18] [17, 19]

There is no antimicrobial that provides ideal coverage for all pathogens at any site of infection. However, moxifloxacin 0.5% ophthalmic solution is a unique, preservative-free antibiotic (thanks to

its concentration it does not require the addition of preservatives to the formula), which offers broad-spectrum activity, and a moderate to high clinical success rate against common ocular pathogens. In addition to this, thanks to its concentration and its high penetrance to the ocular tissues, it allows a dosing regimen at infrequent intervals, simplifying its administration and making it more convenient for patients. [6, 7, 9, 10]

